4.2 Secondary endpoint, objectives and estimands

There is only one secondary outcome:

S1: Readmission due to bacterial infection within 100 days from treatment initiation.

It is defined similarly as the first co-primary outcome (**P1**), but within 100 days instead of 28. The corresponding secondary objectives are to estimate the risk of the outcome under each treatment strategy; as well as the risk differences. The corresponding clinical questions of interest are:

"What are the risks of readmission due to bacterial infection within 100 days from treatment initiation when using the standard and when using the individualized duration, regardless of initiation of any additional interventions during the follow-up, when needed to ensure good clinical care? What is the corresponding risk difference?"

We consider that both the "intention-to-treat" (ITT) and the "Per protocol" (PP) estimands are relevant, as for the first co-primary outcome **P1** and for similar reasons. Accordingly, the corresponding estimands are defined as for **P1** in Section 4.1, except for the endpoint attributes, which are defined by **S1**.

³precisely, time and day of end of treatment or 28 days after first treatment initiation, whichever comes first (because we compute the sum within 28 days).

4.3 Exploratory outcomes

Exploratory outcomes are listed below, in arbitrary order:

E1: Length of initial hospital stay, from onset of first antibiotic treatment to discharge (within 28 days).

E2: Total length of hospital stay (i.e., cumulative, any stay, within 28 days). For the initial stay, the duration is defined as for **E1**. For subsequent stays, if any, we consider the total duration from admission to discharge.

E3: Culture positive infection within 28 days after initial antibiotic treatment started.⁴

E4: Any serious adverse event (SAE) related to the study intervention within 100 days from treatment start, defined as any of these events:

- Bacteremia
- Meningitis
- Culture positive Sepsis
- Culture positive Meningitis
- Death

E5: Total duration of antibiotics use (in hours) within 100 days from treatment start.

E6: Breastfeeding at 2 days after end of initial antibiotic treatment (accepted range 1-3 days).

E7: same as **E6**, but at 21 days instead of 2 (accepted range 17-25 days).

E8: CRP at 2 days after treatment stopped (accepted range 1-3 days).

E9: same as **E2**, but within 100 days instead of 28.

E10: hospital readmission for any cause within 28 days.⁵

E11: same as **E10**, but within 100 days instead of 28.

Remarks: First, computation of **E5** is similar to that of **P2** detailed in Section 4.1.3, within 100 days for **E5** instead of 28 for **P2**. In Denmark, all drug prescriptions from all doctors are registered in the Shared Medication Record (“Fælles Medicinkort”, aka FMK). The necessary data to compute **E5** (and also **P2**) will be extracted from this central registration system. Second, data about **E6** and **E8** are collected during a planned follow-up visit. Third, data about **E7** are collected by phone interviews.

⁴**Note:** about **E3**, we mean a new culture started after inclusion. If the index culture that was negative at inclusion turns positive later, this does not count.

⁵Unlike for the primary outcome, there is no restriction about the admission to define **E10**, except for the admission to be within 28 days.

5 General Considerations

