February 6, 2025

Signature & Date

2 List of Abbreviations

- CI: Confidence Interval
- CRP: C-reactive protein
- GBS: Group B streptococcus
- ITT: Intention-To-Treat
- PP: Per Protocol
- SAE: Serious Adverse Event
- SAP: Statistical Analysis Plan

3 Introduction

This document is the statistical analysis plan (SAP) for an open label, investigator-initiated, parallel group, 1:1 randomized, multicenter, non-inferiority clinical trial of “individualized” versus “standard” duration of antibiotic treatment for culture negative early-onset infection in term newborns. The individualized treatment duration is based on structured clinical assessment of symptoms and level of C-reactive protein (CRP). The individualized treatment duration can be as short as two days while the standard treatment duration is seven days. It is hypothesized that an individualized treatment duration will shorten the duration of antibiotic therapy in newborns with early onset infection with no or very limited increase in the risk of relapse.

The trial recruited newborns from all Departments of Neonatology in Denmark except one (17 out of 18). Stratified randomization was planned 36 to 48 hours after the treatment started using permuted blocks of size six, stratified on maximum CRP level within the last 48h above or below 90 mg/l. Patient accrual started in Spring 2022 and was anticipated to stop in January 2025, after inclusion of 488 newborns.

The changes to the protocol-planned analyses are summarized in Section 12. We do not consider them as major changes and the rationale for each of them is provided.

4 Objectives, Endpoints, and Estimands

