4.1.1 Readmission due to bacterial infection

The first co-primary outcome (**P1**) is hospital readmission due to bacterial infection (or death, although none is expected), within 28 days after treatment started. Specifically, hospital readmission due to bacterial infection is defined as hospital readmission that fulfills all of the following:

¹By regularly we mean every 18 to 48h, typically every 24h, approximately.

²Specifically, seven days in 15 out of 17 departments, including all of the largest; five days in two departments.

- ≥ 1 clinical symptom(s), among those listed in Table 1
- CRP during readmission > 10 mg/l
- ≥ 72 hours of antibiotic treatment received following readmission

Note that there is no minimum time for the time to readmission as we define and record it. A newborn can be readmitted as early as the day of discharge or the following day.

The first co-primary clinical question of interest is: *“Is the risk of hospital readmission due to bacterial infection within 28 days after the start of treatment not more than 4% higher when using the individualized treatment duration than when using the standard duration of seven days, regardless of initiation of any additional interventions during the follow-up, when needed to ensure good clinical care?”*

To answer this question, we will use two co-primary estimands. The first corresponds to an **“intention-to-treat estimand”** and is described by the following attributes:

- Population: infants diagnosed with a probable or possible infection within 0-72 hours from birth according to a structured infection risk assessment, who have received 36 to 48h of antibiotic treatment and no positive blood culture result so far; infants are born with gestational age ≥ 35 weeks and weight ≥ 2000 g.
- Endpoint: hospital readmission due to bacterial infection (as defined above; or death) within the first 28 days after treatment initiation.
- Treatment: The investigational interventions (“individualized” vs “standard”, as defined above) regardless of any subsequent treatment decision or intervention during the follow-up needed to ensure good clinical care and regardless of adherence (“treatment policy strategy”, see [15]).

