5.2 Multiplicity Adjustment

No multiple testing correction will be used, as formal hypothesis testing will be performed only for the primary estimands described in Section 4.1. Although there are two co-primary outcomes with two estimands each and hence four hypothesis tests, no multiple correction is needed. This is

because we require that the two co-primary objectives of the trial have been met to conclude that the trial is positive. This corresponds to an “All-or-none” win criterion [6] and “intersection union test” [1, Sec. 2.2.2]. In addition, we require that both tests, for the ITT and PP estimands, are significant to conclude statistical significance for the corresponding co-primary objective.

Reporting for other endpoints/estimands will be limited to point estimates of effects with 95% (two-sided) confidence intervals. The widths of the intervals will not be adjusted for multiplicity and therefore it will not be possible to use them in place of formal hypothesis testing. This is in line with common recommendations [20].

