5.4 Covariate adjustment

No covariate adjustment will be used in the statistical analysis. Non-parametric unadjusted analyses will be performed instead.

Because randomization was stratified by maximum CRP, covariate adjustment would usually be recommended, especially for the analysis of the co-primary outcomes **P1** and **P2**, as this usually leads to power gains [10, 16]. However, we expect very few hospital readmissions due to bacterial infection (**P1**) in each group, whatever the maximum CRP. This specific context has two important consequences for the analysis of outcome **P1**. First, potential loss of power is expected to be negligible. Second, the typical large sample approximations required to ensure correct coverage probability and type-I error control using a “covariate-adjusted” approach would be very questionable.

Covariate adjustment could also be recommended to make the “no unmeasured confounding” assumption more plausible, for the analysis of the PP estimand using the “Per protocol analysis set” (defined in Section 6). Here again, the rationale for no covariate adjustment is that we expect very few hospital readmissions due to bacterial infection (**P1**), making “covariate-adjusted” inference likely unreliable. Instead, a sensitivity analysis will be provided (see Section 7.1.1). Additionally, descriptive statistics will be provided of newborns included in, and excluded from, the “Per protocol analysis set”. This will facilitate the assessment of the risk of selection bias, which could potentially lead to confounding (see Section 10.2.5).

A very large power is expected for the analysis of the co-primary outcome **P2**, hence there is no real power gain incentive to use covariate adjustment in the analysis of **P2**. Additionally, we are not aware of well-known, model-robust and recommended methods using covariate adjustment to compare medians. Finally, the analysis of **P2** aims to establish superiority and unadjusted ITT analyses are generally conservative when the aim is to show superiority.

6 Analysis Sets

- The “**All participants analysis set**” (**All**) consists of all randomized participants.
- The “**Per protocol analysis set**” (**PP**) consists of all randomized participants that have actually received the intervention (“individualized” or “standard”) as they should according to the protocol. Deviations from the protocol that are used to exclude patients from this analysis sets are listed in Section 10.2.5.

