10.1.3 SAE

To complement the main analysis of **E4** (SAE), we will also compute the risk and risk difference, with 95%-CI, for each possible SAE listed in the definition of SAE. The same statistical methods as those used for the analysis of **E4** (SAE) will be used.

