10.1.4 Cumulative incidence plots

Cumulative incidence curves will be reported, per arm, to describe when each of the following events occurred during the follow-up.

- (I) readmission due to bacterial infection, within 100 days (relevant for **P1** and **S1**)
- (II) culture positive infection within 28 days (**E3**)
- (III) SAE within 100 days (**E4**)

The curves will be estimated by simple empirical (i.e., observed) proportions and pointwise two-sided 95%-CI computed as exact binomial two-sided 95% CIs (computed using the `binom.test()` function of R).

We will perform the analysis using the “All participants analysis set”. We might reproduce the analysis using the “Per protocol analysis set”, if relevant, although we do not expect it will be the case, as we expect very few non adherers.

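### Does footnote 4, which keeps a late-positive index culture out of E3, also need to be written for E4?

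*SAP*

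**What the plan says.** E3 in Section 4.3 is culture-positive infection within 28 days of the start of antibiotics. Footnote 4, which names E3 only, requires a new culture begun after inclusion and adds: "If the index culture that was negative at inclusion turns positive later, this does not count".

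E4 in the same section is any SAE "related to the study intervention within 100 days from treatment start, defined as any of these events". The list that follows is bacteremia, meningitis, culture-positive sepsis, culture-positive meningitis and death. There is no footnote on the index culture.

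The Introduction puts allocation after the start of both windows: "Stratified randomization was planned 36 to 48 hours after the treatment started". The population in Section 4.1.1 is infants "who have received 36 to 48h of antibiotic treatment and no positive blood culture result so far", and the main analysis set in Section 6 "consists of all randomized participants".

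Section 10.1.3 repeats the E4 analysis "for each possible SAE listed in the definition of SAE", and curve III of Section 10.1.4 shows "SAE within 100 days". For outcomes other than the co-primary ones, Section 5.2 states: "Reporting for other endpoints/estimands will be limited to point estimates of effects with 95% (two-sided) confidence intervals".

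**The concern.** A late-positive index culture is foreseeable. Eligibility asks only that no positive result has been reported by 36 to 48 hours, and every randomized infant stays in the intention-to-treat analysis. The authors foresaw the case and ruled it out, but only for E3. A reader who takes the E4 list as the whole definition could count the same sample as bacteremia or culture-positive sepsis. That count would carry over to the per-event estimates in Section 10.1.3 and to the SAE curve.

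At stake is the trial's summary of serious harm. Counting an infection present before allocation would raise the SAE risk in both arms, add noise to the difference and make E3 and E4 disagree about one infant. With few events, a single misclassified infant would be visible in the table.

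**Working it through.** **Reading the two definitions side by side**

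| | E3 | E4 |
|---|---|---|
| Window from treatment start | 28 days | 100 days |
| Must be related to the intervention | no | yes |
| Rule on the index culture | excluded by footnote 4 | none stated |
| Events | culture-positive infection | four infection terms and death |

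E3 has no causal condition, so without footnote 4 a late-positive index culture would count. The footnote is needed there. E4 has a causal condition. The index culture was already negative at inclusion, so it was taken before allocation, and what it shows cannot result from the strategy assigned later. The relatedness condition can therefore do in E4 what the footnote does in E3. The doubt is whether the words that introduce the list override that condition. The SAP does not settle this, but it does not oblige the analyst to count the sample.

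**Size if the literal reading were followed**

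The SAP states no figure that depends on this point, so there is none to reproduce. It gives no SAE rate and no late-positive rate. The event counts below are assumptions; only the 244 infants per arm come from the SAP (Section 11.1).

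Shift in the arm's risk from k added events: k/244.
- k = 1: 1/244 = 0.41 points
- k = 2: 2/244 = 0.82 points
- k = 4: 4/244 = 1.64 points

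The E4 interval is the Miettinen-Nurminen score interval. Its limits are the values d at which (p1 − p2 − d)/√V(d) = ±1.96, where V(d) is the variance at the restricted estimates with p1 − p2 = d.

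| Events, individualized v standard | Difference (points) | 95% CI (points) |
|---|---|---|
| 1 v 1 | 0.00 | −1.91 to 1.91 |
| 2 v 2 (one added per arm) | 0.00 | −2.21 to 2.21 |
| 3 v 3 (two added per arm) | 0.00 | −2.47 to 2.47 |
| 2 v 1 (one added, individualized) | 0.41 | −1.54 to 2.57 |
| 3 v 1 (two added, individualized) | 0.82 | −1.17 to 3.19 |

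Relative width: 2.21/1.91 = 1.16 and 2.47/1.91 = 1.29, so 16% and 29% wider.

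Chance that all T late positives fall in one arm, treating allocations as independent at 1:1: 2 × 0.5^T. For T = 2 this is 0.50; for T = 4 it is 0.125. Either arm is equally likely to receive them, so the expected difference under intention-to-treat is zero. With T = 0 nothing changes.

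**The case for a change.** The strongest case for a change is that the E4 sentence goes on to define the outcome by its list, and the SAP gives no attribution step, onset rule or new-culture rule for it. Because the exclusion is written for E3 alone, a reader might infer that E4 differs on purpose. The remedy would be one sentence, and the culture data are needed for E3 anyway. It stands that the wording is ambiguous. It does not follow that the plan directs a wrong count.

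A second argument concerns the per-protocol set, in which Table 2 also analyses E4. Section 10.2.5 lists overlong treatment as a deviation in the individualized arm and early stopping in the standard arm. If a late-positive result led to treatment more than one day beyond the assigned strategy, such infants would leave the set in one arm and stay in the other. Counting them in E4 would then favour the individualized arm. The logic is sound, but the premise is not in the SAP. The intention-to-treat result is reported alongside, and Section 10.2.5 already calls for a description of those excluded and the reasons.

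Copying footnote 4 to the culture-based components would also not close the gap. Plain meningitis is on the list without a culture requirement, so a pre-inclusion lumbar puncture would raise the same question of timing.

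**Conclusion.** No change to the plan is called for. The SAP leaves a clarification unstated for one exploratory outcome, and an analyst applying the relatedness condition would leave out an infection found only in a sample taken before allocation. E3 and E4 have different windows and event lists and need not agree infant by infant.

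Under the literal reading the cost is 0.41 points of E4 risk per miscounted infant, with no systematic bias under intention-to-treat. P1, P2, S1 and power are untouched, and no test is attached to E4. The planned reporting would also expose a miscount: Section 10.1.3 separates the event types, and curve III would show an SAE in the first days after treatment start.

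This rests on two assumptions: that the relatedness wording is applied as written, or that the protocol (not shown) sets attribution in the usual way; and that late positives are few. The SAP gives no figure for the second.

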5.1 Statistical Hypotheses

The following (confirmatory) 1-sided hypothesis is planned to be tested, in relation to the first co-primary objective (detailed in Sec. 4.1). The aim is to show that “individualized” duration is not unacceptably worse than “standard” duration with respect to readmission due to bacterial infection within 28 days, using a non-inferiority margin of 4%. The aim is to show this using the two estimands: the “intention-to-treat” estimand and “Per Protocol” estimand. Importantly, non-inferiority will only be concluded if both are significant.

- Null hypothesis: the risk of readmission due to infection within 28 days from start of treatment is **at least** 4% higher when using the “individualized” treatment duration than when using the “standard” treatment duration. Formally, $\mathcal{H}_0 : \pi_1 - \pi_0 \geq 4\%$, where π_1 and π_0 are the 28-day risks using “individualized” and “standard” duration, respectively.

versus

- Alternative hypothesis: the risk of readmission due to infection within 28 days is **at most** 4% higher when using the “individualized” treatment duration than when using the “standard” duration. Formally, $\mathcal{H}_1 : \pi_1 - \pi_0 < 5\%$.

The following (confirmatory) 1-sided hypothesis is planned to be tested, in relation to the second co-primary objective (detailed in Sec. 4.1). The aim is to show that “individualized” is better than “standard” with respect to the median of the total duration of antibiotics use within 28 days from treatment start. The aim is to show this using the two estimands: the “intention-to-treat” estimand and “Per Protocol” estimand. Importantly, superiority will only be concluded if both are significant.

- Null hypothesis: the median of the total duration of antibiotics use within 28 days from start of treatment is **larger** when using the “individualized” treatment duration than when using the “standard” treatment duration. Formally, $\mathcal{H}_0 : m_1 > m_0$, where m_1 and m_0 are the median total duration using “individualized” and “standard” initial treatment duration, respectively.

versus

- Alternative hypothesis: the median of the total duration of antibiotics use within 28 days is **smaller** when using the “individualized” treatment duration than when using the “standard” duration. Formally, $\mathcal{H}_1 : m_1 < m_0$.

Operationally, the hypotheses will be evaluated by one-sided tests at 2.5% and matching 95% two-sided confidence intervals.

5.2 Multiplicity Adjustment

No multiple testing correction will be used, as formal hypothesis testing will be performed only for the primary estimands described in Section 4.1. Although there are two co-primary outcomes with two estimands each and hence four hypothesis tests, no multiple correction is needed. This is

because we require that the two co-primary objectives of the trial have been met to conclude that the trial is positive. This corresponds to an “All-or-none” win criterion [6] and “intersection union test” [1, Sec. 2.2.2]. In addition, we require that both tests, for the ITT and PP estimands, are significant to conclude statistical significance for the corresponding co-primary objective.

Reporting for other endpoints/estimands will be limited to point estimates of effects with 95% (two-sided) confidence intervals. The widths of the intervals will not be adjusted for multiplicity and therefore it will not be possible to use them in place of formal hypothesis testing. This is in line with common recommendations [20].

5.3 Missing Data

No missing data are expected for co-primary outcome **P1**, as the investigators have access to all relevant data from all hospital admissions (and deaths) occurring in Denmark. In Denmark, these data are registered centrally. The same naturally holds for **S1**, **E10** and **E11**.

No missing data is anticipated either for co-primary outcome **P2**. As already mentioned in Section 4.3, in Denmark, all drug prescriptions from all doctors are registered in the Shared Medication Record (“Fælles Medicinkort”, aka FMK). The investigators will extract the necessary data to compute **P2** (total duration of treatment within 28 days) and **E5** (total duration of treatment within 100 days) from this central registration system. Hence, there will be no missing data.

No missing data is expected for length of hospital stay (neither total length, **E2**, **E9**, nor initial length, **E1**), culture positive infections (**E3**) or SAE (**E4**). However, some missing data are expected for data about breastfeeding (**E6** & **E7**). We might also observe a few missing data for the exploratory outcome CRP at 2 days after treatment stopped (**E8**). The most probable cause of missing data is omission of registration by the treating physician as all infants should be seen and have CRP level checked at that time. More missing data are expected for breastfeeding (**E6**) than for CRP at 2 days (**E8**). This is because data collection about breastfeeding needs the treating clinicains to write down the information, whereas data collection about CRP at 2 days is automated. The assumption of the data being missing completely at random is considered realistic for exploratory outcome **E6** and **E8**. Data collection for **E7** was planned via phone interviews. Missing data completely at random is also considered realistic for **E7**.

Note that data about breastfeeding and CRP outcomes collected at follow-up visits (**E6**, **E7**, **E8**) will be considered as missing if the visit occurs outside of the accepted range (1-3 days for the “visit at 2 days”; 17-25 days for the “visit at 21 days”). However, no visit or very few are expected to occur outside the accepted ranges.

